3.4.5.2. Blinding

Investigative personnel who are involved in the preparation/application and removal of the treatments (CCP-020 [Diacerein 1%] topical ointment and vehicle ointment) will be unblinded and will not perform the evaluation of skin responses. The trained evaluator who will be evaluating skin responses will be blinded to IPs and the treatment allocation; however, because of the demarcations/skin coloration remaining on the skin following patch removal, complete blinding of the evaluators cannot be completely assured.

Investigative personnel, including the Investigator and the trained evaluator involved in the evaluation of responses, will remain blinded during the course of the study until Database Lock and finalization of the Statistical Analysis Plan (SAP).

In the event of an emergency, if possible, the Investigator or designee will contact the Sponsor with notification of the intent to unblind the treatment codes prior to the actual unblinding. If it is not possible to notify the Sponsor prior to the unblinding, the Investigator or designee will contact the Sponsor immediately following the unblinding procedure and follow with a written notification to document the exact manner in which the code was broken and the justification for the unblinding. The Investigator will communicate the treatment identification to only the investigative personnel who require the information to manage the emergency. Unblinding will happen on site at TKL.

3.4.6. Prior and Concomitant Therapy

All medications, including over the counter (OTC) drugs and vitamins, taken within 28 days prior to the start of the study will be recorded at Screening. Thereafter, a record of all medications taken during the course of the study will be made. Information regarding the total daily dose, route of administration, start and discontinuation dates, and indication are to be captured on the subject's CRF.

The following prohibitions will apply for the duration of the study:

- There will be no use of systemic/topical anti-inflammatory analgesics which in the opinion of the investigative personnel will interfere with the study results, including anti-inflammatory medications such as aspirin (81 mg aspirin will be allowed at the discretion of the Investigator), Aleve, Motrin, Advil, or Nuprin for 72 hours prior to and during the study (occasional use of acetaminophen will be permitted);
- There will be no use of systemic/topical corticosteroids within 3 weeks prior to and/or during the study;
- There will be no use of systemic/topical antihistamines 72 hours prior to and during the study;
- There will be no use of medication known to cause phototoxic reactions (e.g., tetracyclines, thiazides, nonsteroidal anti-inflammatory drugs (NSAIDs));
- There will be no use of medication which, in the opinion of the Investigator, will interfere with the study results (e.g. anti-inflammatory medications, antipsychotics, anticonvulsants with potential pain relief effects, immunomodulatory medications, and others);

- There will be no use of sunbeds or sunlamps or deliberate exposure of the test sites to natural sunlight or to other sources of UV light;
- There will be no participation in any other clinical study;
- There will be no soaking of test areas; and/or
- There will be no application of any product to the test areas.

The use of or change in the dose of any and all concomitant medication, either prescription or OTC, during the study will be recorded. The reason for use or change of dose of a concomitant therapy may need to be reported as an AE. Therapies (medication and non-medication therapies) not restricted by the protocol may be used. Non-prohibited chronic therapies being used at Baseline may be continued.

All topical or systemic medication listed in the exclusion criteria are prohibited during this study.

See the IB for information about possible drug-drug interactions.¹

3.4.7. Treatment Compliance

All patches will be applied and removed by investigative personnel. Whereas bathing will be allowed (low tub bath/frontal showers), the patched areas are not to be soaked and are to be kept as dry as possible, per the instructions to be given to each subject. Subjects will be instructed to contact the Investigator before starting any medication, including OTC remedies. In the case of an emergency treatment, the Investigator must be informed as soon as possible. A trained, experienced evaluator will assess study compliance.

Records of patch applications and visit schedule compliance will be recorded on the subjects' CRFs.

3.5. Visit Schedule and Assessments

3.5.1. Study Procedures and Visit Schedule

Screening

At Screening, the subjects will receive any necessary written and verbal information, and the informed consent of each subject will be obtained. Demographic data (including Fitzpatrick skin type) will be recorded, a medical history will be taken, and previous and concomitant medications will be reviewed. Eligibility will be determined by review of the inclusion/exclusion criteria.

- Any written and verbal information
- Informed consent
- Demographics
- Previous/concomitant medication
- Review of inclusion and exclusion criteria
- Medical history (including lifestyle and habits)

.

Table 1:	Fitzpatrick Skin Types
Ι	Always burns easily, never tans
II	Always burns easily, tans minimally
III	Burns moderately, tans gradually
IV	Burns minimally, always tans well
V	Rarely burns, tans very well
VI	Never burn, deeply pigmented ^{4,5}

Day 1

On Day 1, all subjects will be questioned regarding the entry criteria and female subjects of childbearing potential will undergo a UPT. If the subject fulfills all the inclusion and none of the exclusion criteria, he/she will be allowed to participate in the study. Concomitant medications and AEs will be reviewed and recorded at this visit.

Upon enrollment, each subject will be assigned a consecutive, unique 3-digit subject number starting with 001, which will correspond to the subject number on the randomization code indicating application placement of the study products.

A baseline evaluation of the patch sites will be performed immediately prior to application of the patches to ensure that no conditions, markings, or coloration of the skin will interfere with interpretation of the study results.

A total of 4 application sites (2 cm x 2 cm each) will be marked on each subject's back, placing 2 sites on opposite sides of the back. Of the 4 sites, 2 will be designated as "irradiated sites" and 2 will be designated as "non-irradiated sites". The CCP-020 [Diacerein 1%] topical ointment and its vehicle ointment will then each be applied to its designated "irradiated site" and its "non-irradiated site" under occlusive conditions. The distance between the patches will be no less than one centimeter. The numbering of the test sites will remain the same throughout the study. The sites will be marked with an indelible, surgical marker.

Minimal Erythema Dose (MED) Determination

On Day 1, subjects will have an area of skin on their back, approximately 50 cm^2 , divided into 6 equal sites marked with a surgical marker. Each of the sites will be irradiated with full spectrum UV light (UVA/UVB), with each exposure differing from the previous by a factor of 1.25 (ie, each irradiated site will be exposed to a 25% greater dose of UV irradiation than the previous site).²

The areas involved in MED determination will be different from the study product application sites. Evaluation of the exposed sites will be performed on Day $2.^3$

Day 2

On Day 2, a trained evaluator will examine the 6 irradiated sites and determine the MED for each subject. To determine the MED the sites are read and scored by the trained evaluator for the presence of erythema. There will be a main evaluator for the study; a backup evaluator will also be assigned in the event that an emergency occurs and the main evaluator is unable to attend the

study visit. The lowest exposure dose of the 6 irradiated sub-sites showing an erythema response is selected as the minimal erythema dose (see Section 3.5.7 for scoring scale).

The clinical staff will remove the patches approximately 24 (\pm 2) hours after application and evaluate the application sites according to the criteria in Table 3 and Table 4 (Section 3.5.7). Evaluations will be recorded on the appropriate CRF. The timing of the UVA and UVA/UVB irradiation will be calculated based on the output of the solar simulator. The solar simulator output will be measured prior to each irradiation. Details of the UV irradiation including output of the simulator, time of exposure, equipment used, and staff performing irradiations will be documented. The sites designated for irradiation will receive 16 J/cm² of UVA radiation followed by 0.5 times the MED of UVA/UVB irradiation, using a filtered light source (see Section 3.5.4). One additional site (untreated) will be irradiated with 16 J/cm² of UVA radiation followed by 0.5 times the MED of UVA/UVB radiation, using a filtered light source and will serve as an untreated control.

In addition, AEs and concomitant medications will be reviewed and recorded, as appropriate.

Day 3

On Day 3, approximately 24 (± 4) hours after irradiation (ie, approximately 48 (± 4) hours following product application) all application sites and the untreated control site will be evaluated. In addition, AEs and concomitant medications will be reviewed and recorded.

Day 4/End of Study

On Day 4, approximately 48 (\pm 4) hours after irradiation (ie, approximately 72 (\pm 4) hours following product application), all application sites and the untreated control site will be evaluated. Adverse events and concomitant medications will be reviewed and recorded, as appropriate. A UPT will be performed for female subjects of childbearing potential.

Retest

Although not all observations of erythema and edema are associated with phototoxicity, erythema and edema must be observed for a reaction to be suspected of being a positive phototoxic reaction. An increase in the intensity of the reaction over time further supports an assessment of phototoxicity. If a reaction is observed at both the irradiated and non-irradiated product sites (ie, if contact sensitization or irritation may have occurred), the reaction upon retest must be at least one grade more intense at the irradiated site than at the non-irradiated site for the reaction to be suspected of being a phototoxicity reaction (refer to Section 3.5.7 for response grades and notations).

If it is determined by the Investigator that a retest should be performed, then the retest patches will be applied as soon as the original reactions have resolved. The Investigator will determine the patch conditions to use during the Retest (see Section 3.4.3). The study material will be applied to naive sites on the back, using appropriate patches to further discriminate a phototoxic reaction from an irritation reaction. Identical patches will be applied to sites previously unexposed to the study material. Approximately 24 (\pm 2) hours later one site will be irradiated with 16 J/cm² of UVA followed by ½ MED of UVB radiation using a filtered light source. An additional untreated site will be irradiated with 16 J/cm² of UVA followed by ½ MED of UVB radiation using a filtered light source. An

be evaluated upon patch removal and approximately 24, 48, and 72 hours after irradiation. Concomitant medications and AEs will also be reviewed.

In some cases the retest may be done on the individual ingredients of the products.

3.5.2. Visit Schedule

A summary of the visit schedule and assessments is presented in Table 2.

	Dosing	Phase		
	Day 1	Day 2	Day 3	Day 4
	Screening			EOS
Informed consent	Х			
Inclusion/Exclusion	Х			
Medical history	Х			
Demographic information	Х			
MED irradiation/evaluation	Х	Х		
Randomization (if applicable)	X ^a			
Product application	Х			
Patch Removal		Х		
Application site evaluations	Х	Х	Х	Х
Application site and untreated control		Х		
site irradiation				
Untreated control evaluation		Х	Х	Х
Review of concomitant medications	Х	Х	Х	Х
Review of adverse events		Х	Х	Х
Urine Pregnancy Test	Х			Х

Table 2:Visit Schedule and Assessments

a The randomization will be performed on Day 1 of the study.

Note: The visit schedule may be revised if necessary.

3.5.3. Definition of minimal erythemal dose

Minimal erythemal dose (MED) is defined as the length (in time) of light exposure required to produce a minimal erythema reaction 16 - 24 hours after irradiation using a standardized filtered UV light source that emits UVB (290-320 nm) as part of its emission spectrum.²

3.5.4. Light source

The light source will be a Xenon Arc Solar Simulator (150 W), with UV-reflecting dichroic mirror, UVC-blocking filter, and visible/infrared blocking filter to generate a continuous emission spectrum in the UVA and UVB range (290 to 400 nm).² An additional filter is added during irradiation of the application sites to block UVB radiation allowing only UVA irradiation of the sites. The output is measured daily prior to irradiation using a radiometer/photometer.

3.5.5. Background information

Date of birth, gender, race, Fitzpatrick skin type (see Table 1), and a significant medical history of each subject will be recorded at Screening.

3.5.6. Efficacy Assessments

No efficacy will be assessed in this study.

3.5.7. Safety Assessments

3.5.7.1. Patch Test Site Evaluations

Assessment of the application sites will be done once daily, Days 1-4. Assessment of the untreated irradiated control site will be done once daily on Days 2, 3 and 4.

The symbols listed in Table 3 and their respective numerical equivalents will be used to express the response observed at the time of examination. Additional response notations are presented in Table 4.

Table 3:Response Scores

Response	Symbol	Numerical Equivalent Score
Erythema		
No reaction	-	0
Mild, but definite erythema	+	1
Moderate erythema	++	2
Marked/severe erythema	+++	3
Edema		
No reaction	-	0
Mild, but definite edema	**	1
Definite edema with erosion/vesiculation	***	2

Table 4:Notations

Response/Comment	Notation
Hyperpigmentation	Hr
Hypopigmentation	Но
Vesiculation	V
Papular response	р
Papulovesicular response	pv
Damage to epidermis: oozing, crusting, and/or superficial erosions	D
Itching	Ι
Spreading of reaction beyond patch study site (ie, reaction where material did not contact skin)	S
Follicular irritation with or without pustule formation (folliculitis)	f
Subject absent	Х
Patch dislodged	PD
Not patched	NP
No reaction	0

Before results are interpreted as indicative of phototoxicity, the subject(s) must first be retested to the product(s) to demonstrate that the results obtained are reproducible.

If the non-irradiated study product sites give reactions indicative of significant primary irritancy or prior sensitization, it may not be possible to make any comments about phototoxic potential. In such situations, further routine patch evaluation might be recommended.

Because of the relatively small number of subjects evaluated in this study, it will generally not be possible (except in extreme cases) to categorize a product as having mild, moderate or severe phototoxic potential.

The readings will be made under a standardized white light source. The numerical equivalent scores will be used for calculations.

3.6. Adverse Events

3.6.1. Method of Determining Adverse Events

Safety assessments will include recording AEs reported spontaneously by the subject or collected by the Investigator. AEs will be recorded at each visit throughout the study on the appropriate CRF. Every attempt should be made to describe the AE in terms of a diagnosis. If a clear diagnosis has been made, individual signs and symptoms will not be recorded unless they represent atypical or extreme manifestations of the diagnosis, in which case they should be reported as separate events.

Subjects should be asked whether, since the time of the last observation or visit, they had any of the following:

- Experience any changes in well-being;
- Used any new medications;
- Changed medication regimens (both prescription and OTC); and/or
- Were admitted to a hospital or had any accidents.

All questions should be of a general nature and should not suggest symptoms.

When an AE is suspected, all relevant evaluations will be carried out and appropriate treatment provided. Additional follow-up will be done as necessary (Section 3.6.4) and recorded in the subject's source documents, and the results will be provided to the Sponsor.

For AE definitions and reporting requirements refer to Section 3.6.2 and Section 3.6.3.

Note: Any observed response which can be denoted using the irritation criteria summarized in Table 3 and Table 4 will not be considered an AE. Likewise, any tape-related irritation will only be noted as an AE when all patches are discontinued due to tape reaction around all sites (see Section 3.6.6).

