3.6.2. Adverse Event Definitions

3.6.2.1. Adverse Events

Information about all local and systemic AEs, whether volunteered by the subject, discovered by Investigator questioning, or detected through other means, will be collected and recorded on the AE CRF and followed as appropriate.

An AE is defined as any untoward medical occurrence in a patient or clinical investigation subject administered a pharmaceutical product (or cosmetic product), which does not necessarily have a causal relationship with this treatment. An AE can therefore, be any unfavorable and unintended sign, symptom, or disease temporally associated with the use of a medicinal investigational product, whether or not considered related to the medicinal investigational product.

Adverse Events will be coded using an internationally recognized medical dictionary for regulatory activities (MedDRA).

Medical conditions/diseases present before starting study treatment are considered AEs only if they worsen after starting study treatment (any procedures specified in the protocol). Any AEs occurring before starting study treatment but after signing the ICF are recorded on the Medical History/Current Medical Conditions CRF.

To the extent possible, each AE will also be described by:

- 1. its duration (start and end dates),
- 2. the severity grade (mild, moderate, severe),
- 3. its relationship to the study drug,

- 4. the action(s) taken, and
- 5. as relevant, the outcome.

Note: Any observed response which can be denoted using the irritation criteria summarized in Table 3 and Table 4 will not be considered an AE. Likewise, any tape-related irritation will not be noted as an AE.

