3.6.4. Adverse Event Follow-up

Any ongoing AE at the time of study completion or withdrawal will be followed until the AE is resolved or the subject is referred to his/her own PMD. The Investigator and the Sponsor will

decide if longer follow-up is appropriate on a case-by-case basis. Subjects who experience any clinically significant AE will remain under medical supervision until the Investigator or the Sponsor's Medical Monitor deems the AE to be resolved, stabilized, or no longer serious enough to warrant follow-up.

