3.6.6. Expected Adverse Events

Any observed response in the patch test area that can be denoted using the irritation criteria summarized in Table 3 and Table 4 will not be considered an AE.

Tape related reactions will only be recorded as AEs when the subject is discontinued due to tape reaction around all sites. When 1 or 2 sites are experiencing severe tape related reactions, the application site will be stopped and the subject will continue on the study.

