4.3. Subject Populations for Analysis

All subjects who receive treatment will be evaluable for AEs. The evaluation of phototoxicity potential of the study products will be assessed for all subjects completing the study.

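### The rule that no Table 3 or Table 4 response is an AE makes no exception for serious or discontinuation-causing reactions, and the tape-reaction notes conflict

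*Combined protocol and SAP*

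**What the plan says.** **Exclusion.** Section 3.6.1 states: "Any observed response which can be denoted using the irritation criteria summarized in Table 3 and Table 4 will not be considered an AE". Section 3.6.2.1 repeats the sentence. Section 3.6.6 has a narrower form, excluding "Any observed response in the patch test area that can be denoted using the irritation criteria summarized in Table 3 and Table 4".

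**What the tables can denote.** In Section 3.5.7.1, Table 3 runs up to "Marked/severe erythema" (score 3) and to edema with erosion or vesicles (score 2). Table 4 adds ungraded signs, including vesiculation, epidermal damage and spread beyond the patch.

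**General collection rule.** Section 3.6.2.1 also says that "Information about all local and systemic AEs, whether volunteered by the subject, discovered by Investigator questioning, or detected through other means", is to be collected and recorded.

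**Rules that depend on AE status.** Section 3.6.2.2 defines an SAE as an AE that meets one of six criteria. Section 3.6.3 requires SAEs to be reported within 24 hours. Section 3.6.4 says "Any ongoing AE at the time of study completion or withdrawal will be followed until the AE is resolved" or the subject is referred to his or her own doctor. Section 3.3.4 provides follow-up for subjects discontinued because of an AE.

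**Who is analysed.** Under Section 4.3 all treated subjects are evaluable for AEs, but "The evaluation of phototoxicity potential of the study products will be assessed for all subjects completing the study". Section 4.6.1 tabulates scores for Days 2, 3 and 4, again for completers only.

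**Tape.** Section 3.6.2.1 says "any tape-related irritation will not be noted as an AE". Section 3.6.6 says "Tape related reactions will only be recorded as AEs when the subject is discontinued due to tape reaction around all sites". Section 3.6.1 makes a tape reaction an AE when all patches are discontinued because of tape reaction around all sites, and refers to 3.6.6.

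**The concern.** Assessment of AEs is part of the objectives in Section 2, and the study has no efficacy component. Keeping expected graded responses out of the AE tables is ordinary practice when those responses are the endpoint. The difficulty is that the exclusion has no upper limit. It treats mild erythema and an eroded or vesicular reaction alike, whatever the consequence for the subject. An empty AE or SAE listing for local reactions could then reflect the recording rule and not the product.

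The tape notes raise a smaller problem. Staff following the definitions section and staff following the section on expected events would classify the same all-sites reaction differently.

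**Working it through.** The plan gives no figure to reproduce here. Section 4.2 supports 30 evaluable subjects without alpha, power or effect size, and the point does not depend on that number. The check is a count and a side-by-side reading.

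**Step 1. What the exclusion covers.** The maximum Table 3 score is 3 (erythema) + 2 (edema) = 5, so every non-zero combined score from 1 to 5 is excluded. Of the 13 entries in Table 4, nine are clinical signs (Hr, Ho, V, p, pv, D, I, S, f). The other four (X, PD, NP, 0) record absence, patch status or no reaction. All nine signs are excluded.

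**Step 2. Whether another rule brings a severe reaction back in.**

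| Rule | Applies to | Reaches an excluded reaction? |
|---|---|---|
| SAE definition (3.6.2.2) | AEs meeting a criterion | No |
| 24-hour report (3.6.3) | SAEs | No |
| Follow-up of ongoing events (3.6.4) | AEs | No |
| Follow-up after discontinuation (3.3.4) | Subjects discontinued for an AE | No |
| AE tables, SAE listing (4.6.2) | AEs, SAEs | No |

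The sentence in 3.6.1 on atypical or extreme manifestations does not help. It concerns when to record signs separately from the diagnosis of something already treated as an AE. Section 3.7.2 names death separately from SAEs, so a death would be reported on any reading.

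**Step 3. Where a severe Table 3 or 4 reaction would appear.**

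| Subject | CRF | AE/SAE tables | Score tables |
|---|---|---|---|
| Completes | Yes | No | Yes |
| Does not complete | Yes | No | No |

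Section 4.6.1 refers to scores. It does not state a summary of the Table 4 notations, so a sign recorded only as a notation has no stated table even for a completer.

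**Step 4. Tape reactions, with four patched sites (3.1).**

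| Tape reaction | 3.6.1 | 3.6.2.1 | 3.6.6 |
|---|---|---|---|
| 1, 2 or 3 sites | Not an AE | Not an AE | Not an AE |
| All 4; all patches discontinued, subject stays in | AE | Not an AE | Not an AE |
| All 4; all patches and the subject discontinued | AE | Not an AE | AE |

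The three sections disagree only in the all-sites rows. Section 3.6.6 describes handling for one or two affected sites and is silent on three.

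**Step 5. Area.** Section 3.6.6 limits the exclusion to the patch test area; 3.6.1 and 3.6.2.1 do not. Notation S denotes spread beyond the patch, so the sections can also differ on a spreading reaction.

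**The case against.** The strongest reply is that these reactions are the endpoint. They are assessed daily under Safety Assessments, recorded on the CRF, tabulated and analysed. Section 4.6 puts local tolerability beside AEs, so a reader of the safety results sees both. The exclusion is deliberate and stated three times. This stands for completers, and it is why ordinary grades should stay out of the AE tables.

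Nor does the general collection rule in 3.6.2.1 directly contradict the exclusion. The carve-out is in the same section, and local events that the tables cannot denote, such as pain or infection, remain AEs.

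There are also partial routes of capture. Section 3.4.6 says the reason for a concomitant therapy may need to be reported as an AE. Section 3.6.1 has subjects asked about hospital admission and new medication. Section 3.3.3 puts withdrawal reasons on the CRF, and 3.3.4 asks for a final evaluation where possible. One can argue that an outcome such as hospitalization is more than a sign the tables denote. These routes reduce the chance of a miss, but none states that seriousness or discontinuation overrides the exclusion.

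The double gap is narrow. There is a single application, removed at about 24 hours, and only a non-completer falls outside the score tables. On tape, 3.6.1 refers to 3.6.6, which suggests that 3.6.2.1 is the outlier, and known adhesive sensitivity is an exclusion criterion.

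A reader might infer that serious local harm would go unrecorded altogether. The documents do not support that, because the CRF data exist. A reader might also size the gap as one missed case in 30, or 3.3%. That denominator does not fit: the 30 are completed subjects (3.3.1), a subject who stops is not among them, and AEs are assessed in all treated subjects (4.3).

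**Conclusion.** The concern holds in a limited form. Followed literally, the protocol keeps a Table 3 or 4 reaction that is serious or causes discontinuation out of AE and SAE reporting. If the subject does not complete, the reaction is also outside the planned score tables. It is not lost as data. The conclusion rests on a literal reading of the exclusion and on the SAE definition requiring an AE first; an investigator might in practice report such a reaction anyway.

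The tape conflict is a separate and smaller defect. It changes classification only when all sites are affected.

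The documents give no expected frequency for either event, so no incidence can be stated. Neither point alters the comparison of scores among completers. Both concern a stated safety objective and can be settled by wording.

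**What to change.** Reconcile 3.6.1, 3.6.2.1 and 3.6.6 into one recording rule, aligned with 3.6.2.2, 3.6.3 and 3.6.4:

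- Ordinary graded responses are recorded in the score tables only.
- A Table 3 or 4 response that meets a 3.6.2.2 seriousness criterion, or leads to discontinuation, is also recorded and tabulated as an AE, and as an SAE if serious.
- The rule states whether it is limited to the patch test area and how notation S is treated.
- The tape rule is stated once and the other sections refer to it. The sponsor decides which of the three versions applies and covers the three-site case.

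Persistence at the last visit should not be a trigger. Day 4 is an endpoint day, so every non-zero Day 4 grade could become an AE, possibly including grades at the untreated control site.

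The cost is protocol wording, a CRF instruction and possibly a few extra AE lines. The scoring and its analysis are unchanged.
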